X: mandatory; (X): if indicated/if applicable

^a If clinically indicated, additional safety measures can be taken at any other trial visits or at unscheduled visits. In addition, auscultation of the heart and lungs will be performed to check specifically for signs of any heart condition or respiratory disorders

^b Review of acceptable contraceptive methods and recent menstrual history with WOCBP

^c Only SAEs/AESIs will be collected during the follow-up period (FU1-FU4)

^d At SCR, a serum test must be performed. At other visits, a urine pregnancy test will be performed

^e Only for subjects who discontinued during the trial and coming for EAP visit to obtain final safety data (Section 4.7)

^f At any time during the trial starting 2 weeks after vaccination if clinically indicated, e.g. in the presence of COVID-19 typical symptoms

^g Any serum blood or PBMC samples must be taken before vaccination

^h If symptoms persist at Day 8, daily symptoms and temperature will continue to be measured and documented each day until resolved
ⁱ AESIs are not collected until vaccine has been received at visit 1.

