4.6 Unscheduled Visit

Clinically indicated additional visits may be necessary between scheduled visits. Unscheduled visits may be performed, e.g., to repeat laboratory testing or physical exams due to a new development. Examinations performed at unscheduled visits will be documented in the source documents as well as in the respective electronic case report form (eCRF) sections for unscheduled visits.

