8.5 Solicited AEs

In this clinical trial protocol solicited AEs are defined as all symptoms specifically listed in the memory aid provided to the subjects following each vaccination. After vaccination, the subjects are requested to monitor and record local symptoms (i.e., erythema, swelling, induration, pruritus and pain at the injection site) as well as general symptoms (i.e., body temperature increase/pyrexia, headache, chills, myalgia, nausea and fatigue) in the memory aid daily for the day of vaccination and the following 7 days (Days 1 to 8 following vaccination, 8-day period). If symptoms persist at Day 8, daily symptoms and temperature will continue to be measured and documented each day until resolved.

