8.16 Safety Laboratory Measurements

The intensity of laboratory/systemic toxicities measured quantitatively will be graded according to the [Toxicity Grading Scale for Healthy Adult and Adolescent Volunteers Enrolled in Preventive Vaccine Clinical Trials \(FDA, 2007\)](#). The laboratory values provided in this toxicity grading scale serve as guidelines and are dependent upon institutional parameters. Institutional specific toxicity gradings will be included in site specific manuals as needed.

Safety laboratory is determined at SCR and V3 (one-dose vaccination schedule) or at SCR, V3 and V6 (two-dose vaccination schedule) and at any other visit(s) if clinically indicated. If the safety laboratory measurements are performed at a local laboratory, the laboratory normal ranges are provided by the safety laboratory and are filed in the Investigator File. Safety laboratory parameters to be evaluated are:

Hematology:

Red blood cell count, hemoglobin, total and differential White Blood Cell count (WBC), platelet count, Hematocrit, mean corpuscular/cell volume (MCV), mean corpuscular/cellular hemoglobin (MCH), mean corpuscular hemoglobin concentration (MCHC) and red blood cell distribution width (RDW) are routinely performed as part of the complete blood cell count and will be included in the laboratory report.

Serum chemistry:

Total bilirubin, Alkaline Phosphatase (AP), Aspartate Aminotransferase (AST), Alanine Aminotransferase (ALT), serum creatinine, sodium, potassium, calcium, CRP.

Pregnancy test:

A β -human choriogonadotropin (β -HCG) pregnancy test will be conducted for all WOCBP at SCR and prior to each vaccination V1 (one-dose vaccination schedule) or V1 and V4 (two-dose vaccination schedule). At SCR a serum β -HCG pregnancy test will be performed; all other pregnancy tests will be conducted as urine β -HCG tests.

Virology:

The following parameters will only be evaluated during the screening period for assessment of inclusion/exclusion criteria:

Human immunodeficiency virus antibody test (anti-HIV)

HBsAG

HCV

Severe Acute Respiratory Syndrome Coronavirus 2 Testing:

SARS-CoV-2 specific antibody test (at SCR only)

SARS-CoV-2 infection test (according to trial schedule)

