9.9 Intercurrent Events

The following are considered intercurrent events: 1) development of COVID-19 symptoms prior to 2 weeks after the last vaccination (Week 6 in Group 1 and Week 2 in Groups 2 and 3) and having a positive test for SARS-CoV-2 infection, and 2) discontinuation due to AEs from either the second vaccination (Group 1) or the trial. For the primary estimand, the second intercurrent event is not considered as having an impact on the SARS-CoV-2 neutralizing antibody levels and therefore the “treatment policy” strategy will be used. Subjects who come in contact with the virus can have significant interference with the SARS-CoV-2 neutralizing antibody levels and thus will be excluded from the primary analysis. This is equivalent to the “while on treatment” strategy.

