1. Development of COVID-19 symptoms prior to 2 weeks after the last vaccination (Week 6 in Group 1 and Week 2 in Groups 2 and 3) and having a positive test for SARS-CoV-2 infection.

Note, subjects who come in contact with the virus can have significant interference with the SARS-CoV-2 neutralizing antibody levels and thus will be excluded from the primary analysis. This is equivalent to the “while on treatment” strategy.

2. Discontinuation due to AEs from either the second vaccination (Group 1) or the trial (all groups).

Note, for the primary estimand the second intercurrent event is not considered as having an impact on the SARS-CoV-2 neutralizing antibody levels and therefore the “treatment policy” strategy will be used.

Population-level summary:

Group 1 - Geometric mean of SARS-CoV-2 neutralizing antibody titers at 2 weeks after the second vaccination.

Groups 2 and 3 - Geometric mean of the fold increases, defined as the ratio of SARS-CoV-2 neutralizing antibody titer at 2 weeks post single boost vaccination divided by the neutralizing antibody titer at baseline (last measurement prior to ABNCoV2 vaccination).

Rationale for estimand: The primary estimand will allow Bavarian Nordic (BN) in this early phase trial to understand the immunogenic effect of the ABNCoV2 vaccine in subjects treated per protocol specifications to inform future later phase trials.

Secondary Estimands

The secondary clinical questions of interest are:

- What percentage of subjects experience an SAE or AESI assessed as related to trial vaccination within 8 days after vaccination?
- What percentage of subjects experience a Grade 3 or higher AE assessed as related to trial vaccination within 8 days after vaccination?

Treatment Condition: open-label, non-randomized treatment where subjects receive at least one vaccination.

Population: Seronegative (Group 1) or seropositive (Groups 2 and 3) adult subjects who meet all of the inclusion and none of the exclusion criteria for the trial, and have received at least one trial vaccination.

Endpoints: Occurrence of a related SAE, AESI, or Grade 3 or higher AE within 8 days after vaccination.

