1.2 Trial Design

- Open label
- Phase 2
- Safety, tolerability, and immunogenicity trial
- Non-randomized
- 210 healthy, adult volunteers grouped as follows:
 - Group 1: Approx. 30 subjects determined to be seronegative for SARS-CoV-2 antibodies at screening (100 µg dose).
 - Group 2: Approx. 90 subjects determined to be seropositive for SARS-CoV2 antibodies at screening (100 µg dose).
 - Group 3: Approx. 90 subjects determined to be seropositive for SARS-CoV2 antibodies at screening (50 µg dose).

For this trial, in a run-in phase 6 adults (comprising of 3 subjects in each Group 1 and 2) will be vaccinated at 1 clinical trial site in a consecutive manner, with an at least 48 hours interval between the first and second subject of each group, then the third subjects dosed on consecutive days, before opening up to full enrollment of the trial. Safety assessments will be based on

solicited and unsolicited AE data through the first week after first vaccination for all 6 subjects, evaluated by an independent Data Monitoring Committee (DMC). After a positive DMC recommendation, enrollment to the rest of Groups 1 and 2 of the trial will commence. Group 3 subjects will be enrolled after completion of Group 2 enrollment. The total duration of subject participation in the trial will be up to 104 weeks (Groups 2 and 3, one-dose vaccination schedule) or 17 weeks (Group 1, two-dose vaccination schedule). The duration of the trial as a whole ultimately depends on the length of the recruitment period.

A temporary halting or termination for the trial as a whole can be decided in case of:

- an SAE and serious AESI with an at least reasonable possibility of a causal relationship to the administration of ABNCoV2 vaccine
- an unexpected Grade 3 or higher systemic reaction or lab toxicity with at least a reasonable possibility of a causal relationship to the administration of ABNCoV2 vaccine

These parameters are not all-inclusive. Other AEs could occur that would trigger a DMC review. Any member of the DMC, the Principal Investigator (PI) and/or the BN Medical Monitor could request a DMC review based on any observation.

Additional immunogenicity sample collection will be performed at 3 months after the last vaccination for all groups, and 6 months, 1 year, and 2 years for Groups 2 and 3 subjects. SARS-CoV-2 infection testing will be performed through the Active Trial Period if clinically indicated.

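### For Groups 2 and 3, the PCR footnote starts testing at 2 weeks, at odds with its own Visit 2 mark and SAP 1.2, and SAP Section 3 item 6 permits exclusion on untested symptoms

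*Protocol*

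**What the plan says.** **When to test.** In the Groups 2 and 3 schedule (Protocol 1.4), PCR is mandatory at screening and marked as if-indicated, with footnote f, at Visits 2, 3 and 4 and at every follow-up visit. Footnote f reads "At any time during the trial starting 2 weeks after vaccination if clinically indicated, e.g. in the presence of COVID-19 typical symptoms". SAP Appendix 3 repeats both the marks and the footnote. Visit 2 is 7 to 10 days after vaccination; Visit 3, which provides the primary sample, is 12 to 16 days after. SAP 1.2 states "SARS-CoV-2 infection testing will be performed through the Active Trial Period if clinically indicated", and SAP 4.1.3 starts that period at the first vaccination. Protocol 8.16 has no timing rule of its own and refers the infection test back to the schedule.

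**What else allows a test.** Footnote a says "If clinically indicated, additional safety measures can be taken at any other trial visits or at unscheduled visits", and Protocol 4.6 says "Clinically indicated additional visits may be necessary between scheduled visits".

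**What the analysis needs.** In SAP 1.1 the first intercurrent event begins "Development of COVID-19 symptoms prior to 2 weeks after the last vaccination" and also requires a positive test. Protocol 9.9 gives the same definition, ending "Week 6 in Group 1 and Week 2 in Groups 2 and 3) and having a positive test for SARS-CoV-2 infection". SAP 4.2.2 and 4.2.3 require a positive PCR as well. SAP 4.5.3.4 tabulates infections occurring before the 2-week point.

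**What the exclusion list allows.** SAP Section 3 item 6 names either symptoms or infection before the primary sample as a possible reason for removal from the Immunogenicity Analysis Set. The list is introduced as things that may exclude a subject, and a data review meeting approves the final exclusions. Table 1 in the same section names infection only.

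**The concern.** Groups 2 and 3 receive one dose, so the whole interval that matters for the first intercurrent event runs from that dose to the sample 12 to 16 days later. The footnote on the PCR row points sites to the end of that interval, while a mark in the same row and a sentence in SAP 1.2 point to earlier testing. A site could follow either in good faith.

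If a site follows the footnote, a subject with symptoms on, say, day 9 may reach the primary sample untested. The data review meeting must then either keep a possible infection in the fold-increase analysis or remove the subject under item 6 on symptoms alone. The second choice departs from the estimand, which asks for a positive test. It is also unspecific. The solicited general reactions on Days 1 to 8 are "body temperature increase/pyrexia, headache, chills, myalgia, nausea and fatigue", and the documents do not list which symptoms count as typical of COVID-19. A removal under item 6 could therefore be a removal for reactogenicity. The count of infections before 2 weeks would also be incomplete, and a PCR not taken at the time cannot be recovered later.

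**Working it through.** **1. The plan's own precision figure.** Inputs from Protocol 9.2 and SAP Section 6: SD 0.5 on the log10 scale before and after the booster, correlation 0.3, n = 90.
- SD of the log10 ratio = sqrt(0.25 + 0.25 − 2 × 0.3 × 0.25) = sqrt(0.35) = 0.5916.
- 95% half-width = 1.96 × 0.5916 / sqrt(90) = 0.122, as stated.
- At a fold increase of 4 the interval is 4 × 10^(±0.122) = 3.0 to 5.3, as stated.

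**2. Visit days against the footnote.** Two weeks after vaccination is V1 + 14.
- Visit 2 window, days 7 to 10: every day precedes day 14, so the mark and the footnote attached to it cannot both apply.
- Visit 3 window, days 12 to 16: days 12 and 13 precede day 14; days 14 to 16 do not. PCR is therefore available at Visit 3 on many schedules, even on the literal footnote.

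**3. The exclusion rules side by side.**

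| Place | Basis for exclusion | Positive test needed | Test itself dated |
|---|---|---|---|
| Protocol 9.9 | symptoms plus test | yes | no |
| SAP 1.1 | symptoms plus test | yes | no |
| SAP 4.2.2 | symptoms plus PCR | yes | yes, before the 2-week point |
| SAP 4.2.3 | symptoms plus PCR | yes | yes, as worded |
| SAP 3, Table 1 | infection before 2 weeks | not spelled out | no |
| SAP 3, item 6 | symptoms or infection | no | no |

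Item 6 is the only row that openly dispenses with a test.

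**4. A late positive.** Take symptoms on day 10, the sample on day 14 and a positive test on day 15. The subject meets Protocol 9.9 and SAP 1.1 but not SAP 4.2.2. Item 6 can remove this subject today, and so, on a natural reading, can Table 1. If item 6 is tightened, SAP 4.2.2 should no longer be stricter than Protocol 9.9.

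**5. Effect of retained infections (illustration).** Let k of 90 subjects be infected and retained, each with an extra 4-fold rise; k and the rise are assumptions. The fold increase becomes 4 × 4^(k/90).
- k = 1: 4.06. Shift on the log10 scale = (1/90) × 0.602 = 0.0067, and 0.0067 / 0.122 = 5% of the half-width.
- k = 3: 4.19. Shift = (3/90) × 0.602 = 0.020, and 0.020 / 0.122 = 16% of the half-width.

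**6. Effect of symptom-only removals on precision (illustration).** If 5% to 30% of 90 were removed (assumed), n falls to 86 to 63 and the half-width rises from 0.122 to between 0.125 and 0.146.

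**The case against.** The best reply is that the intended rule can be recovered and the consequences are slight. The Visit 2 mark, SAP 1.2 and the planned table of infections before 2 weeks all presuppose early testing, which leaves one footnote out of step. Intercurrent illnesses are recorded as adverse events from consent through the end-of-active-phase visit, so symptomatic subjects would still come before the data review meeting. Item 6 only permits exclusion. Exclusion reasons are reported, and SAP 4.2.3.1 repeats the analysis on the Safety Analysis Set, so symptom-only removals would be visible.

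Most of this stands, and it rules out several stronger readings that a reader might infer:
- *Infections before the primary sample cannot be confirmed.* Visit 3 carries a PCR mark, Protocol 9.9 does not date the test, and footnote a and Protocol 4.6 leave room for earlier measures and visits. The footnote is not a ban.
- *Most of the interval is closed to testing.* On the literal footnote alone, min(14, d)/d for a sample on day d of 12 to 16 gives 88% to 100% of the interval without a direction to test. That figure sets aside the Visit 2 mark and SAP 1.2, and the documents do not settle which governs.
- *Item 6 forces out subjects with vaccine reactions.* It does not; the meeting decides.
- *SAP 4.2.2 loses late positives.* Section 3 can already remove them.

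What the reply does not answer is that permission is not direction. Footnote a is attached to the examinations, vital signs, ECG and safety laboratory rows, not to the PCR row, and Protocol 8.16 sends the site back to the schedule. The sensitivity analysis shows what symptom-only removals did, but it cannot identify infections that were never tested.

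**Conclusion.** The point holds as a minor inconsistency that is cheap to remove. Two conflicts of wording are certain from the current text: footnote f against its own Visit 2 mark and SAP 1.2, and item 6 against the positive-test requirement in Protocol 9.9 and SAP 1.1, 4.2.2 and 4.2.3. Followed literally, the footnote means that early infections in Groups 2 and 3 may be confirmed late or missed.

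The numerical consequence is small. The shift from 4.0 to between 4.06 and 4.19 rests on assumed values for both the number of retained infections and their extra rise. The trial is descriptive, so no test result turns on it. The case for acting is that membership of the primary analysis set should follow the stated estimand, in an analysis that SAP 4.6 treats as final for Groups 2 and 3 and uses to inform phase 3.

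**What to change.** 1. In Protocol 1.4 and SAP Appendices 2 and 3, change footnote f so that clinically indicated PCR applies from the day of vaccination.
2. Together with step 1, change SAP Section 3 item 6 to require a positive SARS-CoV-2 test. The two belong together: until early testing is directed, item 6 is the only listed route for dealing with a symptomatic, untested subject. Keep Table 1's exclusion of infection before the 2-week point.
3. As an alignment note, let SAP 4.2.2 and 4.2.3 follow Protocol 9.9: symptom onset before the primary sample with a confirming positive test counts even if the test falls after the 2-week point. Do not add a limit on days from onset to test; Protocol 9.9 has none, and a limit would narrow the intercurrent event.

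The cost is wording in two documents plus some extra symptom-triggered PCRs of a type already scheduled, many of them prompted by vaccine reactions. If 10% to 30% of subjects were tested (assumed), that is 0.10 × 90 = 9 to 0.30 × 90 = 27 tests per group of 90.

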2.1 Introduction to SARS-CoV-2 Virus

SARS-CoV-2 infection, which causes coronavirus disease 2019 (COVID-19), is an ongoing worldwide public health emergency. The SARS-CoV-2 virus is not only highly infectious, but infections may lead to humoral immune responses with low virus neutralizing capacity (Chen et al., 2020, Robbiani et al., 2020, Wu et al., 2020).

SARS-CoV-2 entry into cells occurs through interaction of the virus spike receptor binding domain (RBD) with the angiotensin-converting enzyme 2 (ACE2) protein on human cells. Upon binding, ACE2 acts as a receptor and human proteases are recruited to mediate cell entry (Shang et al., 2020a).

In convalescent COVID-19 patients, despite generally low humoral responses, neutralizing antibodies specific to the RBD of SARS-CoV-2 are recurrently found (Robbiani et al., 2020). Interestingly, SARS-CoV-2 may be more effective in evading an effective immune response than SARS-CoV-2 (the coronavirus that causes SARS) because the SARS-CoV-2 spike more frequently assumes a conformational state that hides the spike RBD (Shang et al., 2020b, Walls et al., 2020, Wrapp et al., 2020). Therefore, displaying the spike RBD of SARS-CoV-2 in a manner that facilitates recognition by the immune system is likely to be protective against COVID-19.

2.2 ABNCoV2 Vaccine

[REDACTED]

[REDACTED]

[REDACTED]

ABNCoV2

92000036

Clinical Trial Protocol

ABNCoV2-01

Edition 3.0

[REDACTED]

[REDACTED]

[REDACTED]

[REDACTED]

[REDACTED]

2.3 Summary of Nonclinical Studies with ABNCoV2 Vaccine

The immunogenicity of ABNCoV2 has been demonstrated in mice (Fougeroux et al., 2021) and in non-human primates (NHP). A single intramuscular (IM) administration of 100 µgABNCoV2 induced SARS-CoV-2 neutralizing antibodies in NHP at comparable levels as found in human convalescent samples, while neutralizing antibody titers induced by 15 µg ABNCoV2 remained below convalescent levels. A second administration of 15 or 100 µg ABNCoV2 led to a >50-fold increase in titers. While 15 µg ABNCoV2 administered 2-times to NHP resulted in significantly reduced lung viral load after SARS-CoV-2 challenge compared to nonvaccinated control animals, the higher dose of 100 µg ABNCoV2 administered 2-times was more effective in that the majority of animals were completely free of virus in lung and also in nasal swabs, demonstrating complete protection. Therefore, the high dose administered 2-times has been chosen to be evaluated in seronegative subjects in the phase 2 trial (a single high dose boost regimen will be administered to seropositive subjects).

The safety and good tolerability of 100 µg ABNCoV2 (adjuvanted in a squalene in water emulsion) administered 2- or 3-times in rabbits was shown in a Good Laboratory Practice (GLP) compliant repeat dose toxicity and local tolerance study, that did not raise any safety concerns for human use.

The ABNCoV2 dose administered to rabbits translates to a human equivalent dose based on body surface area (FDA, 2005) of 774 µg for a 60 kg human; this provides a safety margin of >7x higher than the 100 µg human dose. Even when taking into account an offset between laboratories using different reagents to determine the ABNCoV2 protein concentration, a potentially lower dose of 70 µg instead of 100 µg used in the toxicity study translates to a human equivalent dose of 542 µg for a 60 kg human and still provides a safety margin of >5x higher than the 100 µg human dose in this phase 2 trial. Further, the number of vaccine applications (3) was in excess of the 1-2 administrations planned in this phase 2 trial, thereby providing an additional safety margin.

See further details in the current effective ABNCoV2 IB.

2.4 Clinical Trial Data with ABNCoV2 Vaccine

To date, no clinical trials with ABNCoV2 vaccine have been completed. A first in human trial is currently ongoing (COUGH-1, EudraCT no. 2020-004621-22/ NCT04839146), and has recruited first subjects in mid-March 2021. In a predefined dose escalation, SARS-CoV-2 naïve subjects will receive up to 70 µg of the ABNCoV2 vaccine in this phase 1 trial. Preliminary safety results in 45 subjects dosed up to 70 µg did not show any relevant safety findings. No final results from this trial are available yet. For further dose justification, please refer to [Section 2.3](#).

2.5 Rationale

SARS-CoV-2 infection, which causes COVID-19, is an ongoing worldwide public health emergency. The SARS-CoV-2 virus is not only highly infectious, but infections may lead to humoral immune responses with low virus neutralizing capacity (Chen et al., 2020, Robbianiet al., 2020, Wu et al., 2020).

Despite the recent approval of several SARS-CoV-2 vaccines using different technologies, such as mRNA-based or adenovirus-vectored vaccines, there is still substantial spread of COVID-19 disease and related disease burdens. These burdens include fatal outcomes as well as the need for continued lockdown or social distancing measures, causing a high economic and societal impact.

The recent emergence of variant strains with yet unknown susceptibility to the currently available vaccines highlights the potential need for continuous adaptation of vaccines and the necessity to administer re-vaccinations (boosts) in populations considered at relevant risk.

Based on the assumption that large parts of the population will obtain at least an initial SARS-CoV-2 vaccination regimen in the coming months, potential medical need is expected to be related to the availability of boost vaccinations for seropositive subjects in order to maintain or adapt immunogenicity to continuously circulating strains of SARS-CoV-2.

This trial will, therefore, evaluate an initial two-dose vaccination regimen of ABNCoV2 in seronegative subjects as well as single dose boost regimens at two different strengths (50 ug and 100 ug/dose) of ABNCoV2 in seropositive subjects. This will provide meaningful insights into the safety, tolerability and immunogenicity of both vaccination regimens, and will confirm whether a single dose boost regimen in seropositive subjects will elicit a comparably high immune response as expected for the two-dose regimen based on the available nonclinical data.

